#### 3.3.2 Cost and utilization (H3).

The H3 cost analyses – comparing healthcare utilization costs related to emergency room and inpatient visits in the observation period by treatment arm – will be carried out using data from the subset of ITT patients who have HealthPartners insurance. Descriptive statistics will be used to compare the characteristics of patients by insurance status and treatment arm, and to summarize utilization (e.g., proportion of patients with a post-index inpatient stay) and cost (e.g., median cost of ED visits) outcomes overall and by treatment arm. Secondary H3 analyses may be conditioned on pre-index patient characteristics that differ by treatment arm.

H3 predicts that patients accrued from CI-CDS clinics will have lower post-index health care utilization costs related to emergency room and inpatient visits, relative to those accrued from UC clinics. Anticipating a zero-mass of patients with no emergency department or inpatient costs, we will employ a 2-part model to test H3. In the first part, the probability that patients will experience one or more emergency department visits or inpatient stays will be assessed using logistic regression in the same form as was used for H1. The second part will employ a generalized linear model (GLM) allowing clustering by clinic and controlling for demographics and baseline risk. Such analyses often specify a gamma distribution for health care expenditures with a log link function of the explanatory variables. We will choose the distribution family based upon the data using a modified Park test and choose the link function using a Box-Cox test. If we observe a statistically significant difference in emergency department and inpatient costs in the CI-CDS group, we will use similar methods to assess whether total costs of care, including all outpatient care and pharmacy, are also lower.

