10. DATA COLLECTION AND QUALITY ASSURANCE

10.1 Data Collection Forms

We expect person-based missingness to be extremely rare. Patients are unlikely to be aware that their data are being used for this research. They will not be consented and are unlikely to request that their data be excluded from analyses. Only patients who have requested that their data not be used for research and appear on site-maintained opt out lists will be excluded.

The primary data source for hypotheses 1 and 3 and the safety analyses will be EHR- and claims-based data repositories maintained by HealthPartners. The stored EHR data elements

required for calculating the primary and secondary outcomes are extracted from live production tables. Medical care costs for H3 will come from administrative claims systems that are relied upon for reimbursement of medical care services. The absence of documentation of a care process, vital sign, or medication should not be interpreted as a missing value but rather as indicative of a care process or test not having been performed or medication not prescribed within the health system. Likewise, absence of utilization indicated by billing claims almost always indicates that the utilization (such as a hospitalization) did not occur. Truly missing field-based observations (e.g., CI diagnosis assigned, action not observed) will be extremely rare, undetectable, and assumed to be missing at random. The primary data source for H2 is a survey developed during the R61 phase. The survey will be administered and data stored securely using RedCap.

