## LIST OF ABBREVIATIONS

Abbreviation	Definition
accrual period	time period when patients accrue into the study that begins at the same calendar time when the CI-CDS system is implemented in all clinics at a site and ends at a pre-determined calendar time
CDS	clinical decision support
CI	cognitive impairment
CI-CDS	cognitive impairment clinical decision support system
CONSORT	Consolidated Standards of Reporting Trials
DSMB	Data Safety Monitoring Board
ED	emergency department
EHR	electronic health record
EPIC	common EHR software system used by HealthPartners and other health systems to manage patient health records
GLM	generalized linear model
H<n>	Hypothesis <number>
ICC	intraclass correlation
ICD-10	International Classification of Diseases, 10 th Revision
index visit	first visit during the accrual period at a randomized clinic at which a patient meets all intervention eligibility criteria
intervention period	time period when the CI-CDS interface is operative in intervention clinics that begins at the same time as the accrual period and ends at a set calendar time
ITT	intent to treat
LMM	linear mixed model
MC-PLUS	algorithm developed in the R61 phase to identify patients at high risk of CI diagnosis
MCI	mild cognitive impairment
Mini-Cog	brief screening tool designed to help healthcare providers identify individuals who may have cognitive impairment
MMSE	Mini-Mental State Examination
MMM	Mayo Mini Mental
MoCA	Montreal Cognitive Assessment
NIH	National Institutes of Health
observation period	time period when patient outcome data accumulate that begins at the patient index visit and ends at the end of the intervention period

Abbreviation	Definition
OR	odds ratio
PCC	primary care clinician
PI	principal investigator
ROR	relative odds ratio
RR	risk ratio
SAP	Statistical Analysis Plan
SLUMS	St. Louis University Mental Status
UC	usual care

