#### **2.4.3 H3 outcomes (secondary): Cost and utilization**

Indicators of any use (utilization) of emergency department (ED), inpatient or both facility types between 365 days prior to the index visit and during the observation period, inclusive, will be calculated from data extracted from insurance claims databases. Additionally, the combined costs of ED and inpatient care delivered will be extracted as paid amounts for facility and professional services on ED and inpatient days. The data elements needed to calculate this outcome will be extracted at the conclusion of the observation period from insurance claims databases among ITT patients who have HealthPartners insurance.

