### 5.2 Event-based missingness

Outcomes that assess clinical effectiveness, cost, utilization and safety will be calculated using data extracted from EHR and administrative data sources maintained by HealthPartners. As such, these outcomes will be ascertained identically for all accrued patients in all randomized clinics. Documentation of these outcomes will have occurred in the course of delivering health care (clinical, utilization outcomes) or administering health insurance (cost outcomes) so that records should be reasonably accurate and complete with minimal and randomly missing information. The absence of documentation of an event is virtually always due to it not having taken place. Truly missing field-based observations (e.g., CI diagnosis assigned, documentation not found) will be extremely rare, undetectable and assumed to occur at random. When care is delivered outside the HealthPartners care system, health care claims can document their occurrence for patients who are also HealthPartners insurance members. Missing information due to events for which patients do not seek care or care that escapes documentation in the EHR or claims will be assumed to occur equally across treatment groups. The estimation techniques used in the planned random coefficient models readily accommodate structural variation across observations in the amount of data present (e.g., patients per clinic) and lead to unbiased parameter estimates and accurate standard errors when data are missing at random.

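### H3 sets no membership date, no end of counting at disenrolment and no member-time term, so claims-based cost after a patient leaves the plan can be recorded as zero

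*SAP*

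**What the plan says.** - **Population.** SAP 3.3.2: the H3 cost analysis "will be carried out using data from the subset of ITT patients who have HealthPartners insurance". No date or duration of coverage is attached.
- **Data.** SAP 2.4.3: the H3 data elements "will be extracted at the conclusion of the observation period from insurance claims databases among ITT patients who have HealthPartners insurance".
- **Window.** The SAP List of Abbreviations defines the observation period as the "time period when patient outcome data accumulate that begins at the patient index visit and ends at the end of the intervention period". With 12 months of accrual, this is about 12 to 24 months per patient (SAP 2.1). The end is a calendar date and is not tied to coverage.
- **Outside care.** SAP 5.2: when care is delivered elsewhere, "health care claims can document their occurrence for patients who are also HealthPartners insurance members".
- **Absent records.** Protocol 10.1: "Likewise, absence of utilization indicated by billing claims almost always indicates that the utilization (such as a hospitalization) did not occur". SAP 5.2: "The absence of documentation of an event is virtually always due to it not having taken place". Neither statement is limited to time as a plan member.
- **Equal loss.** SAP 5.2 (and likewise SAP 2.4.5): "care that escapes documentation in the EHR or claims will be assumed to occur equally across treatment groups".
- **Model.** SAP 3.3.2: part 1 is a logistic regression for any ED or inpatient use, in the H1 form. Part 2 is a GLM for cost with clustering by clinic, demographics and baseline risk. The only time offset in the plan is optional and belongs to the primary analysis (SAP 3.2).

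**The concern.** Claims see a patient's ED and inpatient care only while that patient is insured by HealthPartners. A patient who is a member at index and changes insurer at month 4 of a 24-month window leaves 20 months in which claims record nothing. Applying the absent-claims statement as written turns those 20 months into no use and no cost.

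Two things are at stake. First, recorded use and cost are too low in both arms, which matters for the descriptive cost figures. Second, H3 tests whether CI-CDS lowers ED and inpatient cost. If the arms lose members at different rates, the arm that loses more looks cheaper, and with no count of disenrolment by arm a reader could not tell. A significant H3 cost difference also triggers the total-cost analysis in SAP 3.3.2.

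**Working it through.** The documents give no sample size, cost, event rate or disenrolment rate for H3, so there is no H3 figure to reproduce. The sizes below rest on stated assumptions.

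**Assumptions.** Follow-up T is uniform on 1 to 2 years (mean 1.5), from 12-month accrual and a common end date. Disenrolment has a constant hazard λ = −ln(1 − p) for annual rate p. Membership is judged at index, and time after leaving carries no claims. There is no true treatment effect. ED or inpatient events are Poisson at r = 0.5 a year with equal cost per event.

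**Step 1: patient time recorded as zero.** Given T, mean member time is (1 − e^(−λT))/λ, and the proportion who ever leave is 1 − e^(−λT). Both are averaged over T.

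| Annual disenrolment p | Mean member time (years) | Time lost (1 − mean/1.5) | Patients who ever leave |
|---|---|---|---|
| 5% | 1.442 | 3.9% | 7% |
| 10% | 1.384 | 7.8% | 15% |
| 15% | 1.326 | 11.6% | 22% |

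**Step 2: equal loss.** With the same p in both arms, the null cost ratio and the part 1 odds ratio are both 1.00. Recorded use and cost are low in each arm, but the comparison is not biased.

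**Step 3: unequal loss, 10% (UC) against 15% (CI-CDS).**
- Mean cost ratio = 1.326/1.384 = 0.958.
- Recorded any use = r/(r + λ) × (1 − e^(−(r+λ)T)), averaged over T. This is 0.523 with no loss, 0.488 at 10% and 0.470 at 15%.
- Part 1 odds ratio = (0.470/0.530)/(0.488/0.512) = 0.93.
- The any-use ratio is 0.470/0.488 = 0.964, and the ratio of mean cost among users is about 0.994. Their product is 0.958, so most of the bias sits in part 1.

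**Step 4: other assumed losses.** Suppose instead that a fraction d of members leaves at a uniform time within follow-up. The mean cost ratio is then (1 − d₁/2)/(1 − d₀/2), with d₁ for CI-CDS and d₀ for UC.

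| Loss, UC vs CI-CDS | Mean cost ratio | Part 1 odds ratio (0.3 to 0.8 events a year) |
|---|---|---|
| 5% vs 10% | 0.974 | 0.94–0.96 |
| 5% vs 15% | 0.949 | 0.88–0.93 |
| 10% vs 20% | 0.947 | 0.89–0.93 |

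Swapping the arms reverses the direction.

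**Step 5: which correction removes the bias.** I simulated the Step 3 null case. In part 1, a complementary log-log link with a log(member time) offset gives a ratio of 1.00, and a log(member time) covariate also removes the bias. In part 2, which models cost among users only, the ratio is about 0.99 uncorrected and 1.00 with a log(member time) covariate. A log(member time) offset there moves it to about 1.04. Cost given at least one event does not grow in proportion to time: a user observed for 4 months with one admission still has one admission's cost. An offset in part 2 would therefore add a larger bias in the opposite direction.

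**The case against.** **The plan does not order zero-scoring.** A reader might infer that the documents instruct analysts to score non-member months as zero. They do not. The protocol sentence says almost always, sits in a general section on data sources and does not discuss leavers. Zero-scoring is what follows when that sentence is applied to patients insured at index. This stands, and it limits the claim to a gap whose default result is zero cost.

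**The membership date is not wholly open.** H3 in the SAP Introduction speaks of HealthPartners-insured patients at elevated risk at index visits, and SAP 2.4.4 lists insurance status among characteristics taken on or before index, though for heterogeneity groups. Both point to index. A reader might take the extraction wording in SAP 2.4.3 to mean that membership is judged at the end, which would drop patients who died or left. That is the weaker reading. Requiring coverage throughout is also possible and would select after randomisation, but no text asks for it.

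**Equal loss is assumed, and no mechanism for unequal loss is documented.** It is tempting to conclude that H3 is tilted towards CI-CDS because new diagnoses prompt patients to change insurer. Nothing in the documents says so. The 10% against 15% illustration is also demanding on that route. It means 14.6% against 21.6% ever leaving, 7.0 points apart, whereas the planned median effect is 19.8 − 12 = 7.8 extra diagnosis points. About nine in ten of the extra-diagnosed patients (7.0/7.8) would have to leave. With 10% background loss, diagnosis uniform over follow-up and departure on the day of diagnosis, the false cost reduction is about 0.4% if 10% of them leave, 0.8% if 20% leave and 3.8% if all leave. Earlier diagnosis would raise these figures. So the bias between arms may well be small. What remains is that the assumption is never checked.

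**Follow-up is partly handled.** Protocol section 8 follows patients unless they die or leave the care system. Leaving the insurer is a different event, and the H3 model does not use that provision. The SAP safety window stops at the earlier of death and the end of observation (SAP 4.2); H3 has no counterpart.

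**The total-cost trigger.** It needs a statistically significant difference. No type I error was computed, so a false trigger is possible but not demonstrated.

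**Conclusion.** The gap is real and should be closed before outcome data are extracted. H3 has no explicit membership date, no stop at disenrolment and no member time in either model part, while both documents treat absence as no care. With membership at index, recorded ED and inpatient use and cost are understated in both arms, by about 4% to 12% of patient time at an assumed 5% to 15% annual disenrolment.

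Bias between arms is conditional. It needs unequal disenrolment, can run either way and is modest over the ranges tried: a cost ratio of about 0.96 and a part 1 odds ratio of about 0.93 at an assumed 10% against 15% a year. The documents supply no rates, so these are illustrations and not estimates, and they do not show that H3 favours CI-CDS. The finding concerns a secondary outcome and leaves H1 untouched.

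**What to change.** In SAP 2.4.3 and 3.3.2:

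1. Define the H3 set as ITT patients who are HealthPartners plan members on the index date.
2. Count use and paid amounts from index to the earlier of disenrolment and end of observation. State that death is not disenrolment, so a coverage end date caused by death does not stop the window. Show deaths by arm beside H3, because zero cost after death can make an arm look cheaper.
3. Account for member time in both parts. In part 1, use a complementary log-log link with a log(member time) offset, or add log(member time) as a covariate. In part 2, use log(member time) as a covariate and not an offset. The covariate also works if the Box-Cox test selects a link other than log.
4. Report disenrolment by arm, so that the equal-loss assumption can be checked.
5. For H3, limit the reading of absence as no care (Protocol 10.1, SAP 5.2) to member time.

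The cost is SAP wording and one merge with plan membership dates. The documents do not describe such a file, but an insurer should hold one. The corrected analysis assumes that, given covariates, disenrolment is unrelated to later cost. That is weaker than treating uncovered time as free of cost.

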### 3.4 Heterogeneity of treatment effects

Treatment effectiveness may vary as a function of patient characteristics. Secondary H1 analyses will add fixed parameters to the H1 model that assess pre-index patient characteristics (e.g., pre-intervention CI risk), comorbidities (e.g., mental illness, substance use) and utilization

(e.g., number of specialty care visits) as main effects and in interaction with the CI-CDS indicator to assess whether the CI-CDS intervention is differentially effective (i.e., treatment heterogeneity) across patient subgroups, or relatedly, whether the CI-CDS intervention can reduce pre-intervention differences in CI care. Model-estimated treatment effects will be calculated within patient subgroups for the sake of description, and the interaction effect (ROR and 95% CI) interpreted if the omnibus interaction with treatment arm is statistically significant.

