9.5.2 Secondary analyses

Treatment effectiveness may vary as a function of contextual factors or patient characteristics.

Secondary H1 analyses will add fixed parameters to the H1 model that assess contextual factors (e.g., area deprivation index score for home address, median education for Census tract of home address) or patient characteristics (e.g., socioeconomic status, gender, pre-intervention CI risk) as main effects and in interaction with the CI-CDS indicator to assess whether the CI-CDS intervention is differentially effective (i.e., treatment heterogeneity) across patient subgroups, or relatedly, whether the CI-CDS intervention can reduce pre-intervention disparities in CI care.

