**Primary Objective:** To evaluate the effect of the clinical decision support (CDS) tool for identifying and managing cognitive impairment (CI) on rates of CI detection in a pragmatic cluster-randomized trial of primary care clinics randomized to intervention (CI-CDS) or usual care (UC).

**H1:** Patients with elevated CI risk at index visits in CI-CDS compared to UC clinics will have significantly higher rates of CI detection as indicated by EHR documentation of CI diagnosis in up to 24 months of follow up.

**Secondary Objectives:** To assess the extent to which the CI-CDS system increases clinician confidence in diagnosing and managing CI, or changes in healthcare utilization costs.

**H2:** Clinicians at CI-CDS compared to UC clinics will have significantly more confidence in diagnosing and managing CI, as assessed through clinician surveys.

**H3:** Among a subset of HealthPartners-insured patients with elevated CI risk at index visits, those at CI-CDS clinics will have significantly lower healthcare utilization costs

related to emergency room and inpatient visits in the follow-up period compared to similar patients at UC clinics.

Treatment effectiveness may vary as a function of contextual factors or patient characteristics. In secondary analyses, contextual factors and patient characteristics will be assessed for the extent to which the CI-CDS system is differentially effective (i.e., treatment heterogeneity) across patient subgroups, or relatedly, whether the CI-CDS intervention can reduce pre-intervention differences in CI care across patient characteristics.

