### 3.2 Primary effectiveness analysis

The H1 effectiveness analyses – comparing likelihood of CI recognition across treatment arms – will be carried out using the ITT sample data: patients accrued from CI-CDS and UC clinics who are at elevated risk for CI but without a CI diagnosis prior to their index visit and not on a research exclusion list. Descriptive statistics will be used to characterize, overall and by treatment arm, the proportion of ITT sample patients who have CI recognized during the observation period, the time elapsed between study accrual and recognition and the clinic intraclass correlation in CI recognition. H1 will be tested using a generalized linear mixed model (LMM) to account for clustering within randomized clinics and normalize the binary outcome via a distribution-appropriate link function (e.g., logit, log). The model will include fixed effects for clinic-randomized treatment group and any patient covariates (e.g., age, sex, predicted risk score) and a random clinic intercept:

$$\text{logit}(\text{diagnosis}_{ji}) = \gamma_{00} + \gamma_{10}\text{CI-CDS}_j + \gamma_{0*}(\text{pt covars})_{ji} + [v_j], \quad \text{where } j=\text{clinic, } i=\text{patient.}$$

Parameter  $\gamma_{10}$  is expected to be positive and statistically significant, indicating that patients in clinics randomly assigned to CI-CDS are more likely to receive a CI diagnosis in the observation period than patients in UC clinics. Model-estimated outcomes will be calculated by treatment group, and the treatment effect will be presented as an odds ratio (OR, or risk ratio [RR]) and its 95% confidence interval.

A secondary model will add a fixed coefficient that represents time elapsed between the index visit and the first EHR-documented CI diagnosis, or zero for those lacking a CI diagnosis, and the interaction between treatment group and time. The time covariate will be coded as (days since index)/365 so that it quantifies the predicted annual change in CI diagnosis rates. The time parameter is expected to be near zero and not statistically significant. Should the time elapsed between index and CI diagnosis differ by treatment group, log (observation time) may be included as an offset in the primary analysis.

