Based on these data-informed estimates, we used the following assumptions regarding the primary effectiveness study for the power analysis: 30, 34 or 38 clinics randomly assigned 1:1 to CI-CDS or UC,  $n=100$  patients per clinic,  $ICC_{clin}=(0.03, 0.04, 0.05)$  and diagnosis rates = (8%, 12%, 16%) in UC clinics. The correlated sample size estimate,  $N$ , was divided by the design effect ( $deff$ ;  $1+(n-1)*ICC$ ) to estimate an effective independent patient sample size (i.e.,  $N_{eff}=N/deff$ ). The power analysis (power=0.80,  $\alpha_2=0.05$ ) estimated the minimum detectable CI-CDS CI diagnosis rate from a single binary predictor in a logistic regression model using the downwardly adjusted effective sample size.

Given the median assumptions for number of randomized clinics,  $ICC_{clin}$  and CI diagnosis rate, the study is powered to detect a diagnosis rate of 19.8% in CI-CDS clinics relative to 12% in UC clinics (Table 1). The absolute increase in diagnosis rates ranges from 5.6% (38 clinics,  $ICC_{clin}=0.03, 8\%$ ) to 10.2% (30 clinics,  $ICC_{clin}=0.05, 16\%$ ) across the range of these assumptions.

**Table 1.** Minimum detectable rates of CI diagnosis in CI-CDS clinics assuming  $n=100$  accrued patients per clinic, 30-38 clinics,  $ICC_{clin} = 0.03-0.05$  and UC diagnosis rates = 8-16%.

		UC diagnoses (%)		
clinics	$ICC_{clin}$	8%	12%	16%
30	0.03	14.4	19.4	24.2
	0.04	15.3	20.4	25.2
	0.05	16.1	21.3	26.2
34	0.03	14.0	18.9	23.6
	0.04	14.8	19.8	24.6
	0.05	15.5	20.6	25.5
38	0.03	13.6	18.5	23.2
	0.04	14.4	19.4	24.1
	0.05	15.1	20.1	24.9

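### The plan asks whether CI-CDS reduces existing differences in CI care but interprets only a ratio of odds ratios, which can show no change or narrowing while the absolute detection gap widens

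*SAP*

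**What the plan says.** The question appears three times. SAP 1.0 asks "whether the CI-CDS intervention can reduce pre-intervention differences in CI care across patient characteristics", SAP 3.4 asks "whether the CI-CDS intervention can reduce pre-intervention differences in CI care", and Protocol 9.5.2 asks "whether the CI-CDS intervention can reduce pre-intervention disparities in CI care". Each time it stands beside the separate question of whether the tool is differentially effective.

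The method is the same for both questions: add the characteristic and its interaction with treatment arm to the H1 model. SAP 3.4 then says that "Model-estimated treatment effects will be calculated within patient subgroups for the sake of description", with "the interaction effect (ROR and 95% CI) interpreted if the omnibus interaction with treatment arm is statistically significant". Protocol 9.5.2 names no summary statistic.

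SAP 3.4 gives no scale for the descriptive subgroup effects. For the H1 model that it extends, SAP 3.2 says "the treatment effect will be presented as an odds ratio (OR, or risk ratio [RR]) and its 95% confidence interval". SAP 3.2 also plans model-estimated outcomes, but by treatment group and not by subgroup. Neither document plans a risk difference, detection rates by arm and subgroup, or a comparison of the between-group gap across arms. Neither says on which scale a reduction is to be judged.

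**The concern.** Effect modification on the odds scale and a change in the gap between two groups' detection rates are different quantities. They agree when the groups start from the same rate and can part company when they do not. The second question is by construction about groups that differ before the intervention, so unequal starting rates are the case of interest. SAP 3.4 itself names pre-intervention CI risk as a moderator.

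If the ROR is near 1, the interaction will probably be non-significant, and under SAP 3.4 nothing is then interpreted on the differences question. If the ROR is significant and moderately below 1, it would read as narrowing. In either case the shares of patients with detected CI may have moved further apart, and no planned output is certain to show it. At stake is the answer to a secondary question that both documents pose.

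**Working it through.** **1. Reproduce the planned effect.** Inputs from SAP 6.0 (also Protocol 9.2.2), median case: 34 clinics, 100 patients per clinic, ICC 0.04, UC rate 12%, power 0.80, two-sided alpha 0.05.
- Design effect = 1 + (100 − 1) × 0.04 = 4.96.
- Effective N = 3400 / 4.96 = 685.5, or 342.7 per arm.
- Solving a pooled two-proportion test for 80% power gives 19.81%; the plan states 19.8%. All 27 cells of Table 1 reproduce to within 0.05 points.
- OR = (0.198/0.802) / (0.12/0.88) = 1.81. RR = 0.198/0.12 = 1.65.

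**2. Assumed subgroup rates.** The documents give none. I take 8% and 16%, the ends of "diagnosis rates = (8%, 12%, 16%) in UC clinics". In the plan these are alternative scenarios for the whole UC arm, so using them as two subgroups is my assumption.

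**3. Equal odds ratio in both groups (ROR = 1, OR = 1.81).** CI-CDS rate = odds × OR / (1 + odds × OR).

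| Group | UC rate | UC odds | CI-CDS rate | Gain (points) | RR |
|---|---|---|---|---|---|
| Lower detection | 8% | 0.0870 | 13.6% | 5.6 | 1.70 |
| Higher detection | 16% | 0.1905 | 25.6% | 9.6 | 1.60 |
| Gap | 8.0 points | | 12.0 points | | |

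The gap grows by a factor of 1.505 (+51%), with no interaction on the odds scale. The same four rates show no change by OR, a larger gain in the lower group by RR, and a larger gain in the higher group by difference.

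**4. Sensitivity to the OR (8% v 16%, ROR = 1).**

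| OR | Growth in gap |
|---|---|
| 1.2 | +14% |
| 1.5 | +34% |
| 1.59 (lowest implied by Table 1) | +39% |
| 1.81 | +51% |
| 2.21 (highest implied by Table 1) | +69% |

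**5. Sensitivity to the starting rates (OR 1.81).** 8% v 12%: +55%. 12% v 16%: +46%. 12% v 30%: +33%. The cohort contrast in SAP 6.0 (2.3% of all patients, 15.1% with MiniCog<3) would give 12.8 to 20.3 points (+58%), though that cohort is broader than the trial population and the second group is part of the first.

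**6. ROR that keeps the gap at 8.0 points** (OR in the higher-detection group divided by OR in the lower).
- Fix the lower group at OR 1.81 (13.6%). The higher group must be at 21.6%, which is OR 1.447. ROR = 1.447 / 1.810 = 0.80.
- Fix the higher group at OR 1.81 (25.6%). The lower group must be at 17.6%, which is OR 2.46. ROR = 1.81 / 2.46 = 0.73.

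An ROR between that value and 1 looks like narrowing on the odds scale while the gap widens.

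**7. Log link.** A constant RR of 1.65 gives 13.2% and 26.4%, so the gap goes from 8.0 to 13.2 points (+65%).

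**8. Precision.** Assume 3400 patients, an even subgroup split (850 per arm-by-group cell) and no between-clinic variation in the interaction, which is optimistic. The interaction test then has power of about 20% at ROR 0.80 and 35% at ROR 0.73. The arm difference in the gap has SE = √Σ[p(1 − p)/850] ≈ 2.5 points, so the illustrated +4.0 would have a 95% interval of about −0.8 to +8.9 and power of about 37%.

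**The case against.** Several stronger readings are tempting, and the documents do not support them.

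- **That the gap is expected to grow by half.** The +51% rests on whole-arm power scenarios borrowed as subgroup rates. It illustrates a mechanism and its rough size; it does not forecast this trial.
- **That the plan will report equal benefit when the interaction is not significant.** SAP 3.4 says only that the ROR is interpreted when the omnibus test is significant. It does not say what will be concluded otherwise.
- **That the ROR is the only thing produced.** Subgroup treatment effects are planned without a significance condition. As rates or risk differences they would show the gap; as ORs or RRs they would not. The plan does not say which.
- **That the open choice between logit and log link causes the problem.** Step 7 shows the gap also widening under a constant RR. The contrast is between relative and absolute scales, not between the two links.
- **That the absolute gap is the one correct criterion.** Neither document says so. For a characteristic such as pre-intervention CI risk, a wider detection gap may be appropriate targeting, and a raw gap takes no account of different true prevalence.

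It is also fair to say that the added estimate would be imprecise and that this is a secondary analysis. Protocol 9.5.1 rests the effectiveness conclusion on the primary analysis.

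After these objections, it still stands that the plan poses the differences question, names no scale for it, attaches a significance condition to the one quantity it will interpret, and does not commit to the rates that would let a reader see the gap.

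**Conclusion.** The point holds as a gap in a secondary analysis. The ROR is a sound measure of effect modification, but on its own it does not answer whether differences in CI care were reduced. With assumed UC rates of 8% and 16% and a common OR of 1.81, the absolute gap widens from 8.0 to 12.0 points while the ROR is exactly 1. Over the ORs implied by Table 1 the growth is about +39% to +69%, and at OR 1.2 it is +14%. For this pair, holding the gap constant needs an ROR of 0.73 to 0.80. The amounts depend on the assumed rates and OR; in every case worked here with a common OR above 1 the gap widens. The H1 test and its sample size are not affected.

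**What to change.** In SAP 3.4, with a matching line in Protocol 9.5.2:

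1. Keep the interaction test and the ROR for the question of differential effectiveness.
2. Name the characteristics to be used for the question of reducing differences.
3. For each of these, whatever the interaction p-value, report the model-standardised detection rate in each arm-by-subgroup cell (averaged over covariates and the clinic effect), the between-group gap in each arm, and the arm difference in that gap with a clinic-based 95% confidence interval.
4. Require any statement that differences were reduced to give both the relative and the absolute result, and to say so if they disagree. The absolute gap need not be the sole criterion.

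The cost is SAP and protocol wording, plus a standardisation step from a model already being fitted. No new data are needed. The downside is a few more estimates, which will be imprecise and should be read as estimates rather than tests.
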